2.2. Rationale

Seasonal influenza poses continuous threats to human populations and especially to elderly and toddlers. The rapid and constant evolution of influenza viruses likewise poses challenges to the development of vaccines for the prevention and control of influenza. Recent vaccine development efforts have focused on the development of “universal” influenza vaccines; that is, vaccines which could offer protection against multiple influenza subtypes. BiondVax has developed a novel vaccine, M-001, that has been shown in preclinical and clinical trials to stimulate directly the cellular arms of the immune system and indirectly, when used as a primer ahead of a strain-specific boost, M-001 enhances immunity to strains contained within the boost and to drifted strains. In view of these immunological outcomes and the good safety profile of the M-001 vaccine candidate, the purposes of the study are to determine the safety and clinical efficacy of M-001 in a large population of older adults and elderly. Cell-mediated immunity expected to be induced by the M-001 will also be evaluated based on samples from subset of participants from Cohort 2. Blood samples will be collected from approximately 263 participants receiving M-001 and 87 participants receiving the placebo (to maintain the blinding). The blood samples from all 350 participants will be collected at baseline (visit 1) and on Visit 3 -14 ± 2 days after the day of the Visit 2 (second vaccination).

2.3. Potential Risks and Benefits

2.3.1. Potential Risks

The potential risks of this study are mostly those associated with having blood drawn and receiving an IM injection that may result in injection site or other adverse reactions, and risk associated with swab collection.

Drawing blood may cause transient discomfort and fainting. Fainting is usually transient and managed by having the subject lie down. Bruising at the blood draw site may occur, but can be prevented or lessened by applying pressure to the draw site for several minutes. IM injection also may cause transient discomfort and fainting. Drawing blood and IM injection may also cause infection. The use of sterile technique will make infection at the site where blood will be drawn or where the study vaccination is given extremely unlikely.

Six previous trials in which approximately 460 participants received M-001 intramuscularly have been completed to date in addition to 2027 who participated in season 1 of the current trial (see Investigator Brochure). AEs described following receipt of M-001 have been similar to those seen in placebo recipients. These included rhinitis/nasal congestion, malaise, myalgia, sore throat, injection site pain and erythema, cough, headache, diarrhea, neck pain, fever, back pain, arthralgia, nausea, vomiting, rash, flushing, dizziness and decreased blood pressure. Analgesics (e.g., acetaminophen, or ibuprofen or similar non-steroidal anti-inflammatory drugs (NSAIDs)) and rest may generally relieve or lessen these reactions. Bruising can sometimes occur due to the vaccination procedure. There were no treatment related SAEs.

The procedure for collection of an NP, deep nasal or throat swab is associated with a slight discomfort, and may, in some instances, cause watering of the eyes or gag reflex. Other than that, there is little to no risk involved.

It is unknown if the M-001 vaccine poses any risks to an unborn child. Female subjects of childbearing potential who are not surgically sterile via tubal sterilization, bilateral oophorectomy, hysterectomy, or successful Essure[®] placement, or who are not postmenopausal for ≥ 1 year must agree to practice highly effective contraception that may include, but is not limited to, abstinence from intercourse with a male partner, monogamous relationship with a vasectomized partner, male condoms with the use of applied spermicide, intrauterine devices, and licensed hormonal methods, with use of a highly effective method of contraception for a minimum of 30 days prior to study product exposure and agree to practice highly effective contraception for the duration of study product exposure, including 2 months (defined as 60 days) after the last study vaccination. A highly effective method of contraception is defined as one which results in a low failure rate when used consistently and correctly. In addition to contraceptive use, all female subjects of childbearing potential will be required to have a negative serum or urine pregnancy test within 24 hours prior to receiving each dose of study vaccine. Urine pregnancy test must be completed within 24 hours prior to vaccination for women of childbearing potential. If urine pregnancy test is positive, subject is not eligible unless serum pregnancy test is negative. If a female subject becomes pregnant while participating in this study, she will be asked for permission to follow-up with her about her health and the health of her baby through pregnancy outcome.

Subjects will be asked to provide personal health information (PHI). All attempts will be made to keep this PHI confidential within the limits of applicable laws including European Union General Data Protection Regulation 2016/679 (GDPR) where applicable. However, there is a chance that unauthorized persons will see the subjects' PHI. All records will be kept in a locked file cabinet or maintained in a locked room at the participating sites. Electronic files will be password protected. Only people who are involved in the conduct, oversight, monitoring, or auditing of this study will be allowed access to the PHI that is collected. Any publications from this study will not use information that will identify subjects by name. Organizations that may inspect and/or copy research records maintained at the participating sites for quality assurance and data analysis include groups such as EMA and local regulatory authorities.

There may be other unknown risks, discomforts, or side effects.

2.3.2. Known Potential Benefits

There are no known benefits attributable to the receipt of the M-001 vaccine, but there is a prospect of benefit. It is possible that vaccination with M-001 will prime the participant for improved responses to future seasonal or pandemic influenza vaccines.

There may be influenza preparedness benefits to society in the future if the M-001 is shown to have a long-lasting efficacy based on the improved cellular immune responses to influenza.

3. OBJECTIVES

3.1. Study Objectives

3.1.1. Primary Objectives

Safety

To assess M-001 Safety by solicited local and systemic reactogenicity events occurring within 8 days (day of the vaccination inclusive) following receipt of each of the two doses of M-001 or placebo and to assess SAEs and new-onset of chronic medical illnesses (NOCIs) during period from Day 0 until end of first passive surveillance period in each group. To assess M-001 safety by occurrence of unsolicited AEs from the time of first study vaccination through 22 days after each study vaccination (day of the vaccination inclusive).

Clinical Efficacy

To assess efficacy of M-001 in the prevention of influenza disease by comparing the occurrence of either qRT-PCR or culture confirmed influenza in the M-001 experimental group vs. placebo caused by any influenza A or B virus in association with a protocol defined Influenza Like Illness (ILI)

3.1.2. Secondary Objectives

Clinical efficacy

- Compare the occurrence of culture confirmed influenza in the M-001 experimental group vs. placebo caused by any influenza A or B virus in association with a protocol defined ILI.
- Assess reduction of severity of either qRT-PCR or culture -confirmed influenza illness by the reduction due to M-001 in the average number of days with respiratory or systemic symptoms during the first laboratory-confirmed influenza illness episode.
- To assess proportion of subjects having ILI symptoms in the experimental or control group.

Immunogenicity

- To assess in at least a subset of samples in season 2 the change from baseline in the percentage of CD4+ lymphocytes producing Th1 cytokine (e.g. INF- γ) in response to any of the 9 peptides in M-001. This endpoint will be assessed within a randomly selected subset of participants from pre-selected sites participating to the substudy in Year 2.

3.1.3. Exploratory Objectives

- Incidence of antibiotics use due to post-influenza secondary infections of respiratory tract as evidenced with medical records or declared by the participant

- Incidence of hospitalization associated with the ILI (≥ 15 days after dosing until epidemiological levels of influenza are low as defined by the medical director).
- Incidence of death due to influenza-like illness (≥ 15 days after dosing until epidemiological levels of influenza are low as defined by the medical director) with or without confirmation by viral culture or qRT-PCR analysis.
- To determine the specific influenza strains in confirmed flu cases in experimental and control group

3.2. Study Outcome Measures

3.2.1. Primary Outcome Measures

Safety

- Occurrence of vaccine-related SAEs from the time of the first study vaccination (M-001 or placebo) until end of first passive surveillance period
- Occurrence of NOCIs from the time of the first study vaccination (M-001 or placebo) until end of first passive surveillance period
- Occurrence of solicited injection site and systemic reactogenicity events on the day of each study vaccination through 8 days after each study vaccination (day of the vaccination inclusive)
- Occurrence of unsolicited AEs from the time of first study vaccination through 22 days after each study vaccination (day of the vaccination inclusive)
- Occurrence of all SAEs, regardless of the assessment of relatedness, from the time of receiving the first M-001 study vaccination until end of first passive surveillance period

Clinical Efficacy

- Percentage of either qRT-PCR or culture-confirmed influenza cases in the M-001 experimental group vs. placebo (during period of ≥ 15 days after the second vaccination until epidemiological levels of influenza are low as defined by the medical director) caused by any influenza A or B virus in association with a protocol defined Influenza Like Illness (ILI is defined as symptoms that include one of the respiratory symptoms (sore throat, cough, sputum production, nasal discharge or congestion, wheezing or difficult breathing) and at least one additional systemic symptom [fever (oral temperature $>37.2^{\circ}\text{C}$ for age 50-59, or $>36.7^{\circ}\text{C}$ for age 60 or more, or increased $\geq 1.3^{\circ}\text{C}$ from baseline), headache, myalgia and/or arthralgia, chills, and fatigue (tiredness for at least 12 hours)]. NP or combined nasal and throat swab will be collected from participants who meet the ILI definition within 24 hours from ILI being reported to or identified by study personnel for qRT-PCR analysis of influenza A and/or B virus. PCR confirmed samples will be further analyzed for culture confirmation.

3.2.2. Secondary Outcome Measures

1. Clinical efficacy

- Percentage of culture confirmed influenza cases in the M-001 experimental group vs. placebo (during period of ≥ 15 days after the second vaccination until epidemiological levels of influenza are low as defined by the medical director) caused by any influenza A or B virus in association with a protocol defined Influenza Like Illness. NP or nasal and throat swab will be collected from participants who meet the ILI definitions within 24 hours from ILI being reported to or identified by study personnel for Culture confirmation of influenza A and/or B virus (a nasal and throat sample will be collected if the participant object the NP swab collection), and the samples identified with qRT-PCR as positive for influenza A or B virus will be verified with virus culture
- Average time to all symptoms alleviation/fever resolution in the experimental vs control group expressed as reduction (in group with M-001 vs. control group) of number of days with respiratory or systemic symptoms during the first laboratory-confirmed influenza illness episode. “Alleviation/resolution” time is defined as the first time point at which all of the following influenza symptoms (body aches (myalgia and/or arthralgia), cough, fatigue/tiredness, headache, nasal congestion/ runny nose/ sputum production, wheezing or difficult breathing, chills and sore throat) were absent and fever had resolved, with both (resolution of all symptoms and fever) maintained for at least 1 day.
- Percentage of subjects having ILI symptoms in the experimental or control group

2. Immunogenicity In Sub-Study

- Change from baseline in the percentage of T cell expressing e.g. interferon gamma (IFN-g) in CD4+ PBMCs after stimulation with M-001 16 days after the second dose of M-001 (day of the vaccination inclusive) . This endpoint will be evaluated in a subset of participants in the experimental group and will further be compared to the percentage of T cell expressing e.g. interferon gamma (IFN-g) in CD4+ PBMCs after stimulation in another study.

3.2.3. **Exploratory Outcome Measures**

- Reduction in the proportion of subjects taking antibiotics use due to a post-influenza secondary infections of respiratory tract, due to vaccination with M-001 as compared to the control group. In case of lack of documented medical record subject’s provided information will be sufficient.
- Reduction in the number of hospitalizations associated with ILI episodes, due to vaccination with M-001 compared to Placebo. Hospitalization associated with ILI (≥ 15 days after dosing* until epidemiological levels of influenza are low as defined by the medical director) in the experimental group as compared to the control group.
- Incidence of death due to influenza-like illness (≥ 15 days after dosing* until epidemiological levels of influenza are low as defined by the medical director) in the

experimental group as compared to the control group, with or without confirmation by viral culture and qRT-PCR analysis.

- Define influenza virus subtype in the swab samples to compare the viruses causing disease in the experimental vs control group

* - within exploratory outcome measures, endpoints and objectives: “dosing” to be understood as second vaccination received.; ≥ 15 days after” is to be understood as ≥ 15 days after the second vaccination, including the day of the vaccination.

4. STUDY DESIGN

This is a pivotal, multicentre, randomized, modified double-blind, placebo-controlled phase 3 trial to assess the safety and clinical efficacy of M-001, an influenza vaccine administered intramuscularly twice in older adults and the elderly (≥ 50 years of age) who meet all eligibility criteria.

Subjects will be assigned randomly to 1 of 2 treatment arms (6000 per study arm during the study) to receive two doses of the M-001 vaccine or placebo (saline). Group A will receive two doses of M-001, each containing 1 mg of M-001, on Day 0 and 22. Group B will receive saline placebo on the same days.

Reactogenicity will be measured by the occurrence of solicited injection site and systemic reactions from the time of each study vaccination with M-001 (or placebo) through 8 days after the study vaccination (inclusive of vaccination day). Unsolicited non-serious AEs collected from the time of each study vaccination through approximately 22 days after each study vaccination (day of the vaccination inclusive) will be analyzed separately. SAEs (including AESIs) and NOCIs will be collected from the time of the first study vaccination through the entire trial period.

In cohort 2, immunogenicity testing will be performed and will include performing CMI assays on blood samples obtained immediately at baseline (Day 0) and on samples collected on Visit 3 (referred to as Day 36, taking place 14 ± 2 days since day of the administration of second dose of the vaccine/placebo). At sites participating in the CMI sub-study, data will be obtained from a subset of approximately 263 participants randomly selected from the experimental group and from a subset of 87 participants randomly selected from the placebo group. Cell mediated immune responses to influenza antigens, including epitopes represented in the M-001 vaccine, will be assessed at baseline (Day 0, before vaccination), and at 14 ± 2 days since day of the administration of second dose of the vaccine/placebo (Day 36).

The duration of this trial for each subject will be up to 1 year (reflecting time between vaccination and end of the flu season as stated in the protocol).

For additional details on study procedures and evaluations and study schedule by study visits/days, see Sections 7 and 8 as well as Table 3 and Table 4 – Schedule of events.

5. STUDY ENROLLMENT AND WITHDRAWAL

5.1. Subject Inclusion Criteria

Subjects eligible to participate in this study must meet all of the following inclusion criteria:

1. Male and female subjects 50 years of age (inclusive) or older, willing and able to give and sign the written Informed consent form (ICF) prior to study entry.
2. Able to comply with the trial procedures and be available for all study visits including answering phone calls and coming to the site as defined by the Protocol.
3. Medically stable (subjects may have underlying systemic chronic conditions such as hypertension, diabetes, ischemic heart disease, or hypothyroidism, as long as their symptoms/signs are controlled; if they are on systemic pharmacological treatment for such condition, the treatment must have been stable for at least 3 months preceding vaccination).
4. Women of childbearing potential (not surgically sterile or postmenopausal for greater than or equal to one year) and men must agree to practice adequate effective contraception – barrier or hormone-based methods or intra uterine device (IUD) for women and a condom for males -whose female partner has childbearing potential - throughout the study treatment and for at least up to day 81 (for female) and day 111 (for male) of the trial (i.e. 60 (for females) and 90 (for males) days after the last dose of the IMP). In addition, women of childbearing potential must have practiced the contraception for a minimum of 30 days prior to study product exposure.
5. Female subjects of childbearing potential must have a negative urine or serum pregnancy test within 24 hours prior to both study vaccinations.

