3. Medically stable (subjects may have underlying systemic chronic conditions such as hypertension, diabetes, ischemic heart disease, or hypothyroidism, as long as their symptoms/signs are controlled; if they are on systemic pharmacological treatment for such condition, the treatment must have been stable for at least 3 months preceding first vaccination).
4. Women of childbearing potential (not surgically sterile or postmenopausal for greater than or equal to one year) and men must agree to practice adequate effective contraception - barrier or hormone-based methods or intra uterine device (IUD) for women and a condom for males - whose female partner has childbearing potential - throughout the study treatment and for at least up to day 81 (for females) and day 111 (for males) of the trial (i.e. 60 (for females) and 90 (for males) days after the last dose of the IMP). In addition, women of childbearing potential must have practiced the contraception for a minimum of 30 days prior to study product exposure.
5. Female subjects of childbearing potential must have a negative urine or serum pregnancy test within 24 hours prior to both study vaccinations.

Exclusion criteria

1. History of neurological symptoms or signs, or anaphylactic shock following administration of any vaccine.
2. Known or suspected (or have a high risk of developing) significant impairment/alteration of immune function (excluding that normally associated with advanced age) as judged by PI/SI.
3. Receipt of: a) Current (including within 60 days before Visit 1 or planned during the study) daily use of immunosuppressive drugs: i) systemic glucocorticoids ≥ 10 mg prednisone per day ii) cytotoxic drugs b) Investigational drugs within 30 days before, or planned during, the study c) Blood products within 3 months before, or planned during, the study d) Influenza vaccine within 6 months before the study or planned during the study e) Other vaccines within 30 days before, or planned during, the study.
4. Any serious disease such as: cancer, autoimmune disease, advanced arteriosclerotic disease or complicated diabetes mellitus, chronic obstructive pulmonary disease (COPD) that requires oxygen therapy, acute or progressive hepatic disease, acute or progressive renal disease, or congestive heart failure, as judged by the PI/SI.

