5. An acute illness, which occurred within 1 week before first vaccination, as judged by the PI/SI, or body temperature greater than: for participants age 50-59 37.9°C (axillary or forehead) or 38.4 °C (oral), or 38.9°C (ear/tympanic or rectal); for participants of age 60 or more, greater than 37.2°C (axillary or forehead) or 37.7 °C (oral), or 38.2°C (ear/tympanic or rectal), which occurred within 1 week before first vaccination.
6. Anatomical deficiencies which exclude possibility of taking NP swab or throat and nasal swab.
7. Women who are breastfeeding or planning pregnancy during the period of the study.
8. Institutionalized subjects or subjects unable to come to the study site as expected by the Protocol.

Test product, dose and mode of administration:

M-001 vaccine, 1.0 mg. Administered twice intramuscularly at 21 days interval (recommended range: 21-30 days)

Reference product, dose and mode of administration:

Normal Saline, Placebo. Administered twice intramuscularly at 21 days interval (recommended range: 21-30 days)

Duration of treatment: Approximately 22 (+9) days for 2 vaccination visits. Cohort 2 participants will attend 3 site visits. Subset of Cohort 2 participants will attend , including additional Visit 3 for immunogenicity testing, and remaining Cohort 2 participants will have the third visit as safety assessment focused site visit. The Visit 3 is planned 14±2 days after Visit 2 day. The total duration of this trial for each subject will be up to 1 year. Shall the optional study extension have occurred for the purpose of follow up on efficacy (subject to future protocol amendment), the participants will have no obligation to continue their follow up thru Year 3.

Criteria for evaluation:

Primary endpoint:

Safety

To assess M-001 Safety by solicited local and systemic reactogenicity events occurring within 8 days (day of the vaccination inclusive) following receipt of each of the two doses of M-001 or placebo and to assess SAEs, and new-onset of chronic medical illnesses (NOCIs) during period from Day 0 until end of first passive surveillance period in each group. To assess M-001 Safety by occurrence of unsolicited AEs from the time of first study vaccination through 22 days after each study vaccination (day of the vaccination inclusive).

Clinical Efficacy

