6.2. Modification of Study Intervention/Investigational Product for a Participant

Individuals must meet the appropriate inclusion and exclusion criteria prior to receiving the subsequently scheduled study injections. There will be no replacement of individuals who do not qualify to receive study dose 2. There will be no dose modifications. If a subject's second study vaccination (study dose 2) cannot occur on Day 22, vaccination should be rescheduled to occur within the expected protocol-specified window for that visit (Day 22 + 9 days), if possible.

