8.2.3. Special Assays or Procedures

Cellular (CMI) Studies

Assays to measure T cell responses will be performed by a qualified laboratory. Venous blood samples for isolation of PBMCs will be collected from a subset of cohort 2, immediately prior to the first study vaccination (Day 0, visit 1 in season 2), and approximately 15 days (day of the vaccination inclusive) after the second study vaccination (Day 36, visit 3, season 2).

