14.4. Exclusion of Women, Minorities, and Children (Special Populations)

This trial will be inclusive of all adults who meet the Subject Inclusion/Exclusion Criteria, regardless of religion, sex, or ethnic background. Should the outcome of this trial be deemed acceptable, additional trials may be initiated in other populations.

It is unknown if the M-001 vaccine poses any risks to an unborn child. Female subjects of childbearing potential who are not surgically sterile via tubal sterilization, bilateral oophorectomy, hysterectomy, or successful Essure® placement, or who are not postmenopausal for ≥ 1 year must agree to practice highly effective contraception that may include, but is not limited to, abstinence from intercourse with a male partner, monogamous relationship with a vasectomized partner, male condoms with the use of applied spermicide, intrauterine devices, and licensed hormonal methods, with use of a highly effective method of contraception for a minimum of 30 days prior to study product exposure and agree to practice highly effective contraception for the duration of study product exposure, including 2 months (defined as 60 days) after the last study vaccination (at least up to day 81 of the trial). A highly effective method of contraception is defined as one which results in a low failure rate when used consistently and correctly. In addition to contraceptive use, all female subjects of childbearing potential will be required to have a negative serum or urine pregnancy test within 24 hours prior to receiving each dose of study vaccine. If a female subject becomes pregnant while participating in this study, we will ask her permission to follow-up with her about her health and the health of her baby through pregnancy outcome.

In selected, individual cases, PI, where justified, may accept complete abstinence from sexual activity in women not having male partner as basis for considering such female subject as of no childbearing potential. Rationale for such decision must be available and documented.

Males whose female partner has childbearing potential, if not after vasectomy, must use condoms throughout the study treatment and for at least up to day 111 of the trial 90 days after the last dose of the IMP.

Children will not be included in this trial as presently there are no safety or efficacy data on this regimen in adults. Should the outcome of this trial be deemed acceptable, additional trials may be initiated in other populations.

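### The contraception end days (Day 81 for women, Day 111 for men) do not move with the second dose, and fall 9 to 10 days short of the stated 60 and 90 days when that dose is given on Day 31.

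*Protocol*

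**What the plan says.** Criterion 4 in Protocol 5.1 asks women of childbearing potential, and men whose partners have childbearing potential, to use contraception "at least up to day 81 (for female) and day 111 (for male) of the trial". The same sentence goes on to say that this means "60 (for females) and 90 (for males) days after the last dose of the IMP". The synopsis has the same pairing ("for at least up to day 81 (for females) and day 111 (for males) of the trial").

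Section 14.4 restates it by sex. For women the rule is "including 2 months (defined as 60 days) after the last study vaccination (at least up to day 81 of the trial"; for men it is "for at least up to day 111 of the trial 90 days after the last dose of the IMP". Section 2.3.1 gives the 60-day rule for women with no trial day attached.

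The first vaccination is on Day 0. The second has a range of dates. Section 6.2 places a dose that cannot be given on Day 22 "within the expected protocol-specified window for that visit (Day 22 + 9 days", so as late as Day 31. The synopsis puts it differently: "Administered twice intramuscularly at 21 days interval (recommended range: 21-30 days". Section 5.3.3 allows a second dose outside the window if the sponsor approves. Nothing in the protocol says that Day 81 or Day 111 moves when the second dose is late.

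**The concern.** A fixed day counted from the first dose can equal a fixed interval after the second dose for only one second-dose date. The plan allows a ten-day range of dates, Day 22 to Day 31, yet treats the two as the same thing.

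Participants agree to the criterion at Visit 1, before the date of the second dose is known. Day 81 or Day 111 is then the only end date that can be entered in a calendar. Someone who keeps to it after a late second dose would stop early while the text says the full period has been completed. Men have no stated point of correction: the male rule carries Day 111 wherever it appears, and the counselling steps in sections 7.1, 7.2.1 and 7.2.2 name women only.

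**Working it through.** **Inputs**

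- End days: 81 (women) and 111 (men), from 5.1, the synopsis and 14.4.
- Required interval after the last dose: 60 and 90 days, from the same places.
- Second-dose date: Day 22 to Day 31 (6.2 and 7.2.1), or Day 21 to Day 30 on the interval wording in the synopsis and 11.3.1.
- Day count: the protocol uses two conventions. Section 8.2.3 counts the vaccination day, "approximately 15 days (day of the vaccination inclusive) after the second study vaccination (Day 36, visit 3, season 2": 36 − 22 + 1 = 15. Visits 3 and 4 do not count it: 22 + 14 = 36 and 22 + 180 = 202. Criterion 4 does not say which applies, so both are shown.

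**Reproducing the plan's figures**

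- Second dose on Day 21, dose day not counted: 21 + 60 = 81 and 21 + 90 = 111.
- Second dose on Day 22, dose day counted: 22 + 59 = 81 and 22 + 89 = 111.

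The stated days are therefore reachable at the nominal date. Each convention yields them for one second-dose date and no other.

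**Days covered across the permitted range**

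Days covered = end day − dose day (dose day not counted), or end day − dose day + 1 (counted). Shortfall = 60 or 90 minus days covered.

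| Second dose | Women, not counted | Women, counted | Men, not counted | Men, counted | Shortfall, not counted / counted |
|---|---|---|---|---|---|
| Day 21 | 81 − 21 = 60 | 61 | 111 − 21 = 90 | 91 | 0 / 1 over |
| Day 22 | 81 − 22 = 59 | 60 | 111 − 22 = 89 | 90 | 1 / 0 |
| Day 30 | 81 − 30 = 51 | 52 | 111 − 30 = 81 | 82 | 9 / 8 |
| Day 31 | 81 − 31 = 50 | 51 | 111 − 31 = 80 | 81 | 10 / 9 |

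The shortfall is the same for both sexes because 111 − 81 = 90 − 60 = 30. It grows by one day for each day the second dose is delayed, so it exceeds these figures for a dose approved after the window.

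**Fixed days that would cover the visit window**

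Taking the latest in-window dose and not counting the dose day: 31 + 60 = 91 and 31 + 90 = 121.

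**The case against.** The best reply is that the operative rule is already in the sentence. The 60/90-day interval follows the actual last dose, and the day numbers are introduced as minimums, so a participant dosed on Day 31 who continues to Day 91 or Day 121 satisfies both halves. In 14.4 the female rule leads with the 60-day interval and adds Day 81 only as a parenthetical floor, and 2.3.1 gives the interval alone. The figures are also correct for the nominal schedule under at least one reading, so this is closer to loose drafting than to a miscalculation.

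A second reply is that the protocol uses post-dose day numbers as labels elsewhere. Visit 3 stays Day 36 and Visit 4 stays Day 202 even when a late second dose moves both visits. Read in that way, Day 81 and Day 111 would move too and no gap would remain.

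The first reply limits the consequence and is accepted to that extent: a site that applies the interval gets the full period. It does not make the two dates equal, and a floor of Day 81 or Day 111 is too low for a late dose. The second does not carry over. Visits 3 and 4 each state the interval that governs them and are named visits, whereas criterion 4 gives an end day of the trial, and no text says it shifts. What participants were told cannot be judged, because the consent material is not available here.

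**Conclusion.** The point holds and is minor. For a dose on Day 22 the stated days are 0 to 1 day short of 60 and 90; for a dose on Day 31 they are 9 to 10 days short. Under the 21 to 30 day interval wording the late-end gap is 8 to 9 days. No combination of day count and window in the protocol closes it.

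The gap reaches a participant only if the site or participant follows the trial-day number rather than the interval. The protocol gives no figure for how many participants this could affect; that few women aged 50 or over are of childbearing potential is a reasonable assumption, but men with partners of childbearing potential are bound as well. No endpoint, analysis population or test depends on it.

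**What to change.** In criterion 4 (synopsis and 5.1) and in both sentences of 14.4, delete the trial-day numbers and state one rule: 60 days for women and 90 days for men after the last dose actually received. This is the form the protocol already uses for concomitant medication (6.5: 21 days after the last vaccination day) and for Visit 4 (180 days after it). Say whether the vaccination day is counted.

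If a fixed day is wanted for sites, use Day 91 for women and Day 121 for men, and keep the 60/90-day rule beside it to cover a second dose approved outside the window.

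Make the same change in any participant material that repeats Day 81 or Day 111. The cost is wording in those places; visits, data collection and analysis do not change.
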